8.2.2 Treatment Procedures

The treatment procedures data is presented on the basis of all enrolled patients. They are performed at Visit 2 and 3 (see details in Section 5.2).

Summaries of treatment procedures and supportive measures will be presented by assigned treatment group (test and control). Detailed information regarding the treatment procedures will be presented in listings (i.e. details per patient).

8.2.3 Other Data Summaries

Protocol deviations will be summarized by deviation type and study center.

Concomitant medications will be presented in listings and also summarized by drug category.

Adverse events will be presented in listings and also summarized by event category.

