3.1 Type and Design of Study

This study is a post-market, prospective, split-mouth, controlled, multi-center study. Split-mouth design: each patient receives two treatments that are randomly assigned to either the right or left quadrant of the maxillary or mandibular arches.

- *Test Treatment:* Minimally Invasive Scaling and Root Planing (SRP) and applications of Emdogain®
- *Control Treatment:* Minimally Invasive Scaling and Root Planing (SRP) alone

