7.2 Assessment of Adverse Events

In the event of an adverse event, the Investigator or another suitably qualified clinician who is trained in recording and reporting AEs and have been delegated to this role (such delegation must be captured in the study site delegation log) must review all documentation (e.g., hospital notes, laboratory and diagnostic reports) relevant to the event.

Each adverse event should be assessed for seriousness, relationship to the study device or the procedure, severity and expectedness, as described below, by the Investigator.

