7.2.3 Relationship to the Procedure

The Investigator should assess the relationship of the adverse event to the surgical procedure (i.e. application or reapplication of Emdogain®). The relationship should be assessed using the categories described in Section 7.2.2.

The Investigator shall provide rationale for the assessment of the expectedness in a short narrative on the AE/ADE Report Form.

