7.2.6 Expectedness

If the adverse event is judged to be related to the device, the Investigator will make an assessment of expectedness based on knowledge of the reaction and any relevant product information as documented in the IFU and current protocol. The event will be classed as either;

- **Expected:** the reaction is consistent with the effects of the device listed in the IFU and protocol;
- **Unexpected:** the reaction is not consistent with the effects listed in the IFU and protocol.

The Investigator shall provide rationale for the assessment of the expectedness in a short narrative on the AE/ADE Report Form.

Potential expected adverse events following the application of Emdogain® by type and in order of severity, observed in the clinical trials, are listed below:

Adverse Event type	Adverse Event description
Sensitization	Low rate of sensitization to Emdogain® as a result of repeated use.
Local soft tissue reactions	Local redness, inflammation soreness, gingival irritation, hematoma/ecchymosis, oral candidiasis, tissue necrosis/cratering, angulitis, herpes-like blisters, hypoesthesia (burning and itching reaction on the tongue), oral mucosal reaction, fibrin layer, discoloration.
Local tooth-related reactions	Increased tooth mobility, hypersensitive root surfaces (root sensitivity), pain.
General reactions	Urticaria, itching skin reaction, gastrointestinal disturbances, urogenital disturbances.

Potential expected adverse device effects following the application of PrefGel®:
Reversible and short duration procedure-related dentin hypersensitivity may occasionally occur.

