7.3 Procedure for Reporting Adverse Events

Adverse event reporting will begin at the time a subject provides written informed consent and ends after a subject withdraws from the study or completes the final study visit.

For screen failure subjects, any AEs, ADEs, and DDs that occur from the time of informed consent up until the date on which the subject is deemed ineligible for the study will be recorded on a case report form.

Only one AE/ADE Report Form or SAE/SADE Report Form should be completed per event.

To ensure patient confidentiality, the following reports will include the patient number only.

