Appendix 3 – Treatment Workflow

Appendix 4 – Visual Analog Scale (VAS)

 CR 01/15	Subject Initials:	

 

	1-2 Days after Treatment
	Subject ID:	

 

 

	
	Date:	

 

 

 

 

 

	

Instructions:
 To be completed by the patient
 Complete this page 1 to 2 days after treatment.
 Indicate the level of pain in the area of your mouth treated for the study.
 Please mark the lines as instructed below.

RIGHT side of mouth

Please mark your pain level by drawing one vertical mark | through the line below.

No pain

Worst pain possible

LEFT side of mouth

Please mark your pain level by drawing one vertical mark | through the line below.

No pain

Worst pain possible

 CR 01/15	Subject Initials:	

 

	1 Week after Treatment
	Subject ID:	

 

	

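### The protocol neither requires the quadrant of a local adverse event nor plans a table by test and control quadrant, so local events not measured as endpoints cannot be reliably compared between sides

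*Combined protocol and SAP*

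**What the plan says.** **Design.** Section 3.1 describes a split-mouth study: "each patient receives two treatments that are randomly assigned to either the right or left quadrant of the maxillary or mandibular arches". The test quadrant receives scaling and root planing (SRP), PrefGel and two applications of Emdogain; the control quadrant receives SRP alone.

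**What is assessed for each event.** Section 7.2: "Each adverse event should be assessed for seriousness, relationship to the study device or the procedure, severity and expectedness". Section 7.2.5 adds outcome. Relationship to the procedure is judged against the "surgical procedure (i.e. application or reapplication of Emdogain" (7.2.3), so SRP, which is done on both sides, is not named. Section 7.3 says "Only one AE/ADE Report Form or SAE/SADE Report Form should be completed per event"; the form itself is not reproduced.

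**What is expected.** The table in 7.2.6 lists local soft tissue reactions (among them redness, hematoma, necrosis and blisters) and local tooth-related reactions: "Increased tooth mobility, hypersensitive root surfaces (root sensitivity), pain".

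**What is tabulated.** Section 8.2.3: "Adverse events will be presented in listings and also summarized by event category". The section just before it, 8.2.2, does name the arms: "Summaries of treatment procedures and supportive measures will be presented by assigned treatment group (test and control)".

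**What is already measured by side.** The pain form in Appendix 4 has separate lines, one headed "RIGHT side of mouth" and one for the left, at three time points, and 8.3.3 summarises pain per treatment group. Root dentin hypersensitivity is scored on the study tooth (5.3.7). Gingival margin and bleeding on probing are recorded at six sites per tooth (5.3.2, 5.3.4). Section 8.3.2 presents all three by treatment group.

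**The concern.** Most of the events expected in 7.2.6 occur at the treated site. In a split-mouth trial the opposite quadrant is a randomised control for exactly these events: same patient, same visit, same SRP. To use it, the analyst must know in which quadrant each event occurred and must plan a table that separates the two. The protocol provides for neither.

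The relatedness judgement is no substitute. It is an open opinion: the investigator or a designee opens the allocation envelope (5.2.1), and no masking of those who assess adverse events is described. Procedure also means the Emdogain application only, so an event caused by SRP in the control quadrant has no natural category.

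The contrast has value here. The US instructions for use in Appendix 1 say that adverse events due to Emdogain alone could not be separated from those of the accompanying surgery. Section 3.3 presents the dual application as different from published approaches, so earlier local safety experience may not transfer. Section 8.1 says that further studies will build on this one.

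**Working it through.** **1. Which local events have a comparison by side?**

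| Local event | Side or site required by the protocol | Planned by treatment group |
|---|---|---|
| Pain | Yes (Appendix 4) | Yes (8.3.3) |
| Root hypersensitivity | Yes, study tooth (5.3.7) | Yes (8.3.2) |
| Bleeding on probing, gingival margin | Yes, six sites per tooth (5.3.4, 5.3.2) | Yes (8.3.2) |
| Soft tissue reactions, necrosis, increased mobility, infection | No (7.2, 7.3) | Not named (8.2.3) |

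The gap is the last row.

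**2. What does a category-only table hide?** The plan gives no adverse event rates, so there is no figure to reproduce. For illustration, assume that 10 of 50 subjects have a given local event on one side only and none on both. Let b be the number with the event in the test quadrant only and c the number in the control quadrant only.

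- Category table: (b + c)/50 = 10/50 = 20%, whatever the split.
- Difference in proportions: (b − c)/50.
- Exact two-sided McNemar p: twice the binomial probability of max(b, c) or more out of b + c at one half, capped at 1.

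| b v c | Category table | Difference | Exact p |
|---|---|---|---|
| 5 v 5 | 20% | 0 | 1.00 |
| 8 v 2 | 20% | 12 points | 0.11 |
| 9 v 1 | 20% | 16 points | 0.02 |
| 10 v 0 | 20% | 20 points | 0.002 |

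One published line is compatible with no difference and with a large one.

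**3. How much could a test show?** Assume marginal rates and independent sides. Then the test-only probability is p_T(1 − p_C) and the control-only probability is p_C(1 − p_T). For 20% v 5%, the expected counts in 50 subjects are 50 × 0.20 × 0.95 = 9.5 test-only and 50 × 0.05 × 0.80 = 2.0 control-only. The p-value depends on how 9.5 is rounded: 10 v 2 gives 0.039 and 9 v 2 gives 0.065.

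The chance of exact p < 0.05, summed over the possible numbers of discordant pairs, is shown for 50 subjects and for 42 (15% dropout: 50 × 0.85 = 42.5, rounded down):

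| Assumed rates, test v control | n = 50 | n = 42 |
|---|---|---|
| 20% v 5% | 52% | 42% |
| 10% v 5% | 7% | 5% |
| 5% v 2% | 1.6% | 0.8% |

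Unless an event is common and strongly one-sided, a test will usually miss a difference. The useful output is the discordant counts and an interval, not a p-value.

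**The case against.** The strongest reply is that much of the comparison already exists. Pain and root sensitivity, two of the three expected tooth-related reactions, are collected by side and presented by treatment group, as are bleeding on probing and gingival margin. This stands. A reader might infer from 8.2.3 that the trial has no controlled comparison of local harm, or that relatedness is the only link between harm and treatment. The documents contradict both.

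Second, section 8.2 sets a default of summarising data in each treatment group unless otherwise specified, and grouping by event category need not override it. That is a fair reading, but it does not close the gap. The default can be applied to a local event only if its quadrant is known, and section 7 does not ask for it.

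Third, the adverse event form and the separate SAP promised at the start of section 8 are not in the documents. Either might deal with location, and free text in the listings might mention it. So a reader should not infer that the quadrant is not collected. What can be said is that the protocol does not require it.

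Fourth, this is a pilot of a marketed device, the German-market instructions (Appendix II) call such procedure-related events rare, and a paired test on rare events has little power. This is right about the test, and it is why the proposed table should be descriptive. It does not favour a total that cannot be split by side.

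**Conclusion.** The concern holds in this limited form. Section 7.2 does not require the quadrant of a local adverse event, and 8.2.3 names a summary by event category only. Local events that are not endpoints (soft tissue reactions, necrosis, increased mobility, infection) therefore cannot be reliably compared between the test and control quadrants. Pain, root dentin hypersensitivity, bleeding on probing and gingival margin are outside the point.

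The size cannot be derived from the documents. The 10-of-50 illustration shows only that a category table is blind to direction: differences from 0 to 20 points in favour of the control quadrant give the same line. The rates and counts are assumed, and the power figures also assume independent sides.

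The conclusion rests on the protocol text alone. If the adverse event form already has a location field, only the table is missing. The contrast would describe the whole test regimen, since PrefGel is also applied on the test side only. This is a cheap improvement, not a defect in the primary comparison.

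**What to change.** 1. Record the location of each adverse event as test quadrant, control quadrant, both, elsewhere in the mouth, or systemic. Where the event is already on file, code the side from source notes and from the right and left photographs required at every visit (5.3.9), then map side to treatment from the randomisation. Ideally the coder does not know the allocation.
2. In 8.2.3, tabulate local adverse events by treatment quadrant. For each category give the subjects affected on the test side only, the control side only, both and neither, with a paired 95% CI for the difference in proportions that suits small counts. State that it is read descriptively.
3. Keep systemic events at subject level, without a quadrant.
4. Report how many events have an unknown location.

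The cost is one form field or one coding pass, and one table. The protocol is Version 5.0 of 29 March 2018, while the synopsis has follow-up complete by December 2017. Coding may therefore be retrospective and incomplete, and item 4 shows the reader by how much.

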8.2.4 Subject Disposition

A description of subject disposition falling in various subgroups of interest, such as consented, screen failures, enrolled, withdrawn early, completed study, will be provided by study center. Moreover, a detailed description providing the reason of any screen failures or early withdrawal by subgroup will be done.

8.2.5 Missing Data

Every effort will be made to minimize the amount of missing data. If subjects drop out of the study prior to completing their primary endpoint assessment, every effort will be made to measure their primary endpoint immediately prior to discontinuation if possible.

Techniques for handling missing data and the presence of outliers will be provided in the Statistical Analysis Plan.

8.3 Planned Statistical Analysis

Two analyses will be performed: A primary analysis at 12 months and an interim analysis at 3 months post-surgery. An optional interim analysis at 6 and 9 months post-surgery may also be performed. Descriptive summary statistics will be computed for all endpoints of the primary and interim analysis.

The data of the four study centers will be pooled. Pooling is justified by applying a high degree of standardization of study procedures and investigator training.

8.3.1 Primary Analysis of Primary Endpoint

Change in Clinical Attachment Level (CAL) between the surgery and 12 months post-surgery will be measured as the primary endpoint.

Statistics of the primary endpoint will present the seven-point scales (mean, standard deviation, minimum, 25% percentile, median, 75% percentile and maximum) of the change in CAL on the site of interest for each treatment group.

8.3.3 Interim Analysis of Endpoints

Interim analysis will be performed for all above endpoints between the surgery and 3 months post-surgery. Optional interim analyses will be performed at 6 months and 9 months post-surgery, as applicable.

In addition, the seven-point scales (mean, standard deviation, minimum, 25% percentile, median, 75% percentile and maximum) of the change in pain for each treatment group will be presented at 1-2 days, 1 week and 2 weeks after surgery.

9 Data Management

The general data management procedures are described below, details can be found in the separate Data Management Plan (DMP).

Required clinical data for this study will be collected and recorded in the clinical database using a paper Case Report Form (CRF) for all study subjects from whom informed consent is obtained. Site numbers and subject numbers will be used to track subject information throughout the registry. The Principal Investigator or authorized designee is responsible for the timely completion and signature of all CRFs.

All original CRFs will be retrieved from the site by the study monitor and sent to the data management. Double data entry and computer programmed error checks will be carried out by data management personnel for inconsistent, illogical and/or missing data. If validation of data leads to discrepancies, data management will generate queries. The timely resolution of the queries is under the responsibility of the monitor and the Investigators at site. The query process is an ongoing process starting with the first data entered into the database.

The electronic clinical database used for this study has a security system that prevents unauthorized access to the data and any deletion of data (audit and edit trail). All above mentioned tasks will be carried out according to Straumann Standard Operating Procedures, Protocol Version 5.0, 29-Mar-2018

except for those tasks performed by Straumann contracted Contract Research Organizations (CRO), where the CRO procedures shall be used.

10 Obligations of the Principal Investigator

10.1 Investigator Compliance

The Investigators must work according to standard ethical practice as laid down by their professional body and insert the product according to what is described in the handling procedures and the IFU for the products investigated in this clinical study. In addition they must work in accordance with the "Declaration of Helsinki" (last revision Fortaleza 2013, Appendix 5), the ISO 14155:2011, GCP, and with local legal and regulatory requirements.

The Investigators will ensure that the study is conducted in compliance with this protocol and the Clinical Study Agreement. Furthermore, they are responsible of conducting the informed consent process (section 5.5.1).

11 Study Management

11.1 Regulatory and Ethical Requirements

11.1.1 Informed Consent

Written informed consent will be obtained from all subjects prior to study participation as described in Section 5.1.1.

11.1.2 Institutional Review Board

Prior to initiation of any study procedures, the protocol and informed consent will be submitted to each local Institutional Review Board (IRB) for review and approval. In addition, any amendments to the protocol or informed consent will be reviewed and approved (if necessary) by the IRB. The study will not begin until the required approval from the IRB has been obtained. Any additional requirements imposed by the IRB shall be followed.

The Investigator will provide the appropriate reports to the IRB during the course of the clinical study including the following:

- Informing the IRB of the study progress periodically as required, but at a minimum annually
- Reporting any unanticipated serious adverse device effects within 10 working days of becoming aware of the event

- Reporting any deviations from the protocol that adversely affect the risk/benefit ratio, the rights, safety, or welfare of the participants, or integrity of the study
- Providing any other reports requested by the IRB

11.1.3 Study registration

This protocol will be registered at clinicaltrials.gov at the study start.

11.2 Record Management

The following will be required from the Investigator prior to the initiation of the study:

- A signed confidentiality agreement
- Signed and dated curriculum vitae of the Investigator (s) and a copy of his/her dental license
- Signed Financial Disclosure
- A signed copy of the final protocol and any amendments
- A signed copy of the clinical study agreement with the sponsor
- IRB approval letter and IRB approved informed consent document

11.2.1 Case Report Forms

Required clinical data for this study will be collected using a paper CRF for all study patients from whom informed consent is obtained. Site numbers and patient numbers will be used to track patient information throughout the study to respect confidentiality.

The Principal Investigator or authorized designee will be responsible for the accuracy of the data entered on the CRFs from source documents, query resolution and signature of all CRFs. The Investigator will also allow a Straumann representative and/or regulatory bodies to review the data reported on the CRFs with the source documents as far as is permitted by local regulations.

11.2.2 Source Documents

Source documents are defined as the original point of entry of a specific data point. Source documents will include, but are not limited to, progress notes, electronic data, computer printouts, radiographs, and recorded data from automated instruments. All source documents pertaining to this study will be maintained by the Investigator and made available for inspection by authorized persons.

11.2.3 Records/Data Retention

Original radiographs, photographs, and study documents will be maintained at the study center in a file established for this study. All study documentation needs to be stored at the study center for at least twenty (20) years following the completion of the study, as specified by the sponsor. The Investigator should have access to the study documents in order to answer any queries associated with the study. All other study records will be kept by Straumann once the study has been completed. These records will be maintained at Straumann according to Straumann's Standard Operating Procedures (SOP).

11.3 Monitoring

Straumann will assign a qualified individual to monitor the study.

The study specific monitoring procedures for performing site visits, frequency, data verification, data corrections, adverse event reporting and tracking, device accountability, regulatory documents review, visit communication and reporting are described in the separate Monitoring Plan.

11.3.1 Pre-Study Meetings

After selection of all Investigators, Pre-Study Meetings were conducted during the preparation phase for the study, at congresses, to explain the study requirements and ensure the sites are fully capable and equipped to participate in the study.

11.3.2 Study Initiation Visit

Once a site receives IRB approval and before enrollment in the study starts, the monitor will schedule a site initiation visit in order to make sure all study documents are in place and that all the site personnel that will participate in the study are trained on the study procedures. The monitor will ensure during the study initiation that the Investigator clearly understands and accepts the responsibilities and obligations of conducting a clinical study:

- Understands the clinical protocol and relevant items outlined in the protocol (including inclusion/exclusion criteria, AE and SAE reporting requirements)
- Understands and accepts the obligations to obtain informed consent
- Understands how to document study data (especially the importance of having supporting documentation for AE assessment)

- Understands the information outlined in the Investigator's brochure, including proper device usage
- Understands aspects of study device accountability (i.e. how to obtain the device, how to store the device, how to document device receipt, usage and return)
- Understands and accepts the obligation to obtain IRB review and approval of the protocol and informed consent, and to ensure continuing review of the study by the IRB
- Has adequate facilities and access to an adequate number of suitable subjects to conduct the study

